### **9.3. Clinical Laboratory Tests**

#### **9.3.1. Laboratory Value Definitions**

For numeric laboratory results, the change and percentage change from baseline will be calculated. Baseline will be determined according to Section 4.1.3. If there are multiple values that meet the criteria for baseline, then the central value has priority over the local value. Thereafter, additional rules may be provided after consultation with the medical monitor to delineate which value will be defined as baseline. For crossover subjects, the corresponding new baseline will be defined, when appropriate, as the last available assessment on or before the date of the first nonzero dose of ruxolitinib. This applies to all laboratory assessments.

Laboratory test values outside of the normal range will be assessed for severity based on CTCAE grade or similar criteria where clinical intervention is required for CTCAE grading.

#### **9.3.2. Laboratory Value Summaries**

All test results and associated normal ranges from central laboratories will be reported in SI units. All tests with numeric values will have a unique unit per test. Any laboratory test results and associated normal ranges from local laboratories will be converted to SI units.

For numeric laboratory values, baseline value, postbaseline value, change from baseline, and percentage change from baseline will be summarized by visit. In addition, mean change from baseline will be plotted over time for selected laboratory parameters including WBC, platelet count, hemoglobin, absolute neutrophil count, alanine aminotransferase, aspartate aminotransferase (AST), bilirubin, blood urea nitrogen, and creatinine.

For the laboratory parameters that have CTCAE grading, shift tables will also be presented by treatment group showing change in CTCAE severity grade from baseline to worst grade postbaseline up to the end of randomization period. Separate analyses of laboratory CTCAE grading will be conducted for all subjects, including those who cross over to ruxolitinib from anagrelide and those who continue on ruxolitinib after unblinding. The denominator for the percentage calculation will be the number of subjects in the baseline category.

Categorical laboratory data will be tabulated by visit at baseline and postbaseline visits where appropriate.

## 9.4. Vital Signs

Values at each scheduled visit, change, and percentage change from baseline for vital signs, including systolic blood pressure, diastolic blood pressure, pulse, respiration rate, and body temperature will be summarized descriptively.

Criteria for clinically notable vital sign abnormalities are defined in [Table 1](#). The abnormal values for subjects exhibiting clinically notable vital sign abnormalities will be listed. Alert vital signs are defined as an absolute value outside of the defined range and percentage change from baseline > 25%. The abnormal values for subjects exhibiting alert vital sign abnormalities will also be listed.

**Table 1: Criteria for Clinically Notable Vital Sign Abnormalities**

| Parameter         | High Threshold | Low Threshold |
|--------------------------|-----------------------|----------------------|
| Systolic blood pressure  | > 155 mmHg            | < 85 mmHg            |
| Diastolic blood pressure | > 100 mmHg            | < 40 mmHg            |
| Pulse                    | > 100 bpm             | < 40 bpm             |
| Temperature              | > 38°C                | < 35.5°C             |
| Respiratory rate         | > 24/min              | < 8/min              |

## 10. INTERIM ANALYSES

No interim analysis for efficacy and futility will be conducted in this study.

## 11. CHANGES AND MODIFICATIONS TO THE ANALYSIS PLAN

All versions of the SAP are listed in [Table 2](#).

**Table 2: Statistical Analysis Plan Versions**

| SAP Version | Date        |
|-------------|-------------|
| Original    | 25 JUL 2016 |
| Amendment 1 | 21 DEC 2016 |
| Amendment 2 | 24 SEP 2019 |

### 11.1. Changes to Protocol-Defined Analyses

Not applicable.

### 11.2. Changes to the Statistical Analysis Plan

#### 11.2.1. Amendment 1

The original SAP has been updated to incorporate the Protocol Amendment 1 updates as well as FDA reviewer comments. Specific changes are outlined below:

- [REDACTED]
- [REDACTED]
- The study design has been updated to allow crossover from anagrelide to ruxolitinib after Week 52; analyses related to crossover have been added.
- Sensitivity analyses for the primary and key secondary efficacy endpoints will be performed if JAK2V617 mutation status changes after the randomization.
- Sensitivity analysis planned for the missing data on the primary endpoint has been added.
- Subgroup analyses based on the presence of JAK2V617 mutation, MPL mutation, CALR mutation, and triple-negative status have been added.

### 11.2.2. Amendment 2

Statistical Analysis Plan Amendment 1 has been updated to incorporate the Protocol Amendment 2 updates as well as FDA reviewer comments. Specific changes are outlined below:

- The study design was updated to align the inclusion criteria values for platelet and WBC count and to reflect the options for the open-label treatment phase.
- The per protocol population analyses were updated to exclude subjects with major protocol violations, including those who do not meet the criteria for ET diagnosis or hydroxyurea resistance/intolerance (inclusion criteria 2 and 3) and those who are < 80% compliant during the primary endpoint assessment period (Weeks 32-52) as determined by drug accountability assessment.
- Analyses for the proportion of subjects with CR at Week 32 and the proportion of subjects with PR at Week 32 based on ELN 2013 response criteria were added.
- The grading scale for toxicities not included in CTCAE v4.03 was updated to include Grade 5, death due to AE.
- Prior anagrelide use (yes vs no) was added as one of the stratification factors for randomization and efficacy analyses to address potential bias introduced by enrolling subjects with prior anagrelide use.
- Other minor, administrative changes have been incorporated throughout the Statistical Analysis Plan and are noted in the redline version of the amendment.

## APPENDIX A. RESPONSE CRITERIA FOR ESSENTIAL THROMBOCYTHEMIA

|                           | Criteria   |
|---------------------------|--|
| Complete remission |  |
| A                         | Durable a resolution of disease-related signs including palpable hepatosplenomegaly, large symptoms improvement, b AND   |
| B                         | Durable a peripheral blood count remission, defined as platelet count $\leq 400 \times 10^9/L$ , WBC count $< 10 \times 10^9/L$ , and absence of leukoerythroblastosis, AND |
| C                         | Without signs of progressive disease and absence of any hemorrhagic or thrombotic events, AND  |
| D                         | Bone marrow histological remission defined as disappearance of megakaryocyte hyperplasia and absence of $>$ Grade 1 reticulin fibrosis.  |
| Partial remission  |  |
| A                         | Durable a resolution of disease-related signs including palpable hepatosplenomegaly, and large symptoms improvement, AND  |
| B                         | Durable a peripheral blood count remission, defined as platelet count $\leq 400 \times 10^9/L$ , WBC count $< 10 \times 10^9/L$ , absence of leukoerythroblastosis, AND     |
| C                         | Without signs of progressive disease, and absence of any hemorrhagic or thrombotic events, AND   |
| D                         | Without bone marrow histological remission, defined as the persistence of megakaryocyte hyperplasia.   |
| No response               | Any response that does not satisfy partial remission.  |
| Progressive disease       | Transformation into PV, post-ET myelofibrosis, myelodysplastic syndrome, or acute leukemia c .  |

ET = essential thrombocythemia; IWG-MRT = International Working Group-Myeloproliferative Neoplasms Research and Treatment; MPN-SAF TSS = Myeloproliferative Neoplasm-Symptom Assessment Form Total Symptom Score; PV = polycythemia vera; WBC = white blood cell.

Note: Molecular response is not required for assignment as complete response or partial response. Molecular response evaluation requires analysis in peripheral blood granulocytes. Complete response is defined as eradication of a pre-existing abnormality. Partial response applies only to subjects with at least 20% mutant allele burden at baseline. Partial response is defined as  $\geq 50\%$  decrease in allele burden.

a Lasting at least 12 weeks.

b Large symptom improvement ( $\geq 10$ -point decrease) in MPN-SAF TSS.

[figure not shown]
c For the diagnosis of PV, refer to the WHO 2016 criteria 13; for the diagnosis of post-ET myelofibrosis, refer to the IWG-MRT criteria 12; for the diagnosis of myelodysplastic syndrome and acute leukemia, refer to the WHO criteria.

[figure not shown]
Source: [Barosi et al 2013](#).

## **APPENDIX B. EASTERN COOPERATIVE ONCOLOGY GROUP PERFORMANCE STATUS**

| Grade | Performance Status  |
|--------------|--|
| 0            | Fully active, able to carry on all predisease performance without restriction.   |
| 1            | Restricted in physically strenuous activity but ambulatory and able to carry out work of a light or sedentary nature, eg, light house work, office work. |
| 2            | Ambulatory and capable of all self-care but unable to carry out any work activities. Up and about more than 50% of waking hours.                         |
| 3            | Capable of only limited self-care, confined to bed or chair more than 50% of waking hours.   |
| 4            | Completely disabled. Cannot carry on any self-care. Totally confined to bed or chair.  |
| 5            | Dead.  |

Source: [Oken et al 1982](#).

## APPENDIX E. SAMPLE SAS CODE

Below is the sample SAS code for multiple imputation of the primary endpoint status.

```
PROC MI DATA=ANAL NIMPUTE=5 SEED=8554633463 OUT=ANAL_MI;  
  CLASS Resp Treat JAK2V617F Plat_BS Infection Trauma Anagre_use;  
  MONOTONE LOGISTIC(Resp = Treat JAK2V617F Plat_BS Infection  
    Trauma PLAT WBC Hemoglobin Anagre_use/ details);  
  VAR Treat JAK2V617F Plat_BS Infection Trauma PLAT WBC Hemoglobin  
    Anagre_use;  
RUN;
```

Below is the sample SAS code to analyze the multiple imputed datasets:

```
PROC LOGISTIC DATA=ANAL_MI;  
  CLASS Resp Treat JAK2V617F plat_screen Anagre_use;  
  MODEL Respo = Treat JAK2V617F plat_screen Anagre_use;  
  By _Imputation_;  
  ODS OUTPUT ParameterEstimates=lgsparms;  
RUN;  
  
PROC MIANALYZE PARMS=LGSPARMS;  
  MODELEFFECTS Treat JAK2V617F plat_screen Anagre_use;  
RUN;
```

| Table No.     | Title  | Population | Standard | In-Text    |
|---------------|--|------------|----------|------------|
| 2.1.13        | Sensitivity Analysis of Proportion of Subjects Achieving the Primary Response – JAKV617F Mutation Change                             | ITT        |          |            |
| 2.1.14        | Sensitivity Analysis of Proportion of Subjects Achieving the Primary Response – Multiple Imputation                                  | ITT        |          |            |
| 2.2           | Summary of Duration of Response  | ITT        |          | X          |
| 2.3.1         | Proportion of Subjects Achieving ELN Response at Week 32   | ITT        |          | X          |
| 2.3.2         | Sensitivity Analysis of Proportion of Subjects Achieving ELN Response at Week 32 – JAKV617F Mutation Change                          | ITT        |          |            |
| 2.3.3         | Proportion of Subjects Achieving ELN Complete Response at Week 32  | ITT        |          |            |
| 2.3.4         | Proportion of Subjects Achieving ELN Partial Response at Week 32   | ITT        |          |            |
| [REDACTED]    | [REDACTED]   | [REDACTED] |          | [REDACTED] |
| [REDACTED]    | [REDACTED]   | [REDACTED] |          | [REDACTED] |
| [REDACTED]    | [REDACTED]   | [REDACTED] |          |            |
| [REDACTED]    | [REDACTED]   | [REDACTED] |          |            |
| [REDACTED]    | [REDACTED]   | [REDACTED] |          |            |
| [REDACTED]    | [REDACTED]   | [REDACTED] |          |            |
| [REDACTED]    | [REDACTED]   | [REDACTED] |          |            |
| [REDACTED]    | [REDACTED]   | [REDACTED] |          |            |
| [REDACTED]    | [REDACTED]   | [REDACTED] |          |            |
| [REDACTED]    | [REDACTED]   | [REDACTED] |          |            |
| Safety |  |            |          |            |
| 3.1.1         | Summary of Study Drug Exposure and Compliance in Randomized Phase  | Safety     | X        | X          |
| 3.1.2         | Summary of Study Drug Exposure in All Ruxolitinib Treated Phase  |            |          |            |
| 3.2.1         | Overall Summary of Treatment-Emergent Adverse Events in Randomized Phase   | Safety     | X        | X          |
| 3.2.2         | Summary of Treatment-Emergent Adverse Events by MedDRA System Organ Class and Preferred Term in Randomized Phase                     | Safety     | X        |            |
| 3.2.3         | Summary of Treatment-Emergent Adverse Events by MedDRA Preferred Term in Decreasing Order of Frequency in Randomized Phase           | Safety     | X        | X          |
| 3.2.4         | Summary of Treatment-Emergent Adverse Events by MedDRA System Organ Class, Preferred Term, and Worst CTCAE Grade in Randomized Phase | Safety     | X        |            |
| 3.2.5         | Summary of Grade 3 or Higher Treatment-Emergent Adverse Events by MedDRA System Organ Class and Preferred Term in Randomized Phase   | Safety     | X        | X          |
| 3.2.6         | Summary of Treatment-Related Adverse Events by MedDRA System Organ Class and Preferred Term in Randomized Phase                      | Safety     | X        |            |

| Table No. | Title  | Population | Standard | In-Text |
|------------------|---|-------------------|-----------------|----------------|
| 3.2.7            | Summary of Treatment-Related Adverse Events by MedDRA System Organ Class, Preferred Term, and Worst CTCAE Grade in Randomized Phase                       | Safety            | X               |                |
| 3.2.8            | Summary of Treatment-Emergent Adverse Events With a Fatal Outcome by MedDRA System Organ Class and Preferred Term in Randomized Phase                     | Safety            | X               | X              |
| 3.2.9            | Summary of Treatment-Emergent Serious Adverse Events by MedDRA System Organ Class and Preferred Term in Randomized Phase                                  | Safety            | X               | X              |
| 3.2.10           | Summary of Treatment-Emergent Serious Adverse Events by MedDRA Preferred Term in Decreasing Order of Frequency in Randomized Phase                        | Safety            | X               | X              |
| 3.2.11           | Summary of Treatment-Related Serious Adverse Events by MedDRA System Organ Class and Preferred Term in Randomized Phase                                   | Safety            | X               |                |
| 3.2.12           | Summary of Treatment-Emergent Adverse Events Leading to Dose Interruption by MedDRA System Organ Class and Preferred Term in Randomized Phase             | Safety            | X               |                |
| 3.2.13           | Summary of Treatment-Emergent Adverse Events Leading to Dose Reduction by MedDRA System Organ Class and Preferred Term in Randomized Phase                | Safety            | X               |                |
| 3.2.14           | Summary of Treatment-Emergent Adverse Events Leading to Discontinuation of Study Drug by MedDRA System Organ Class and Preferred Term in Randomized Phase | Safety            | X               | X              |
| 3.2.15           | Summary of Treatment-Emergent Adverse Events Leading to Withdrawal From the Study by MedDRA System Organ Class and Preferred Term in Randomized Phase     | Safety            | X               |                |
| 3.2.16           | Summary of Treatment-Emergent Non-Serious Adverse Events by MedDRA System Organ Class and Preferred Term in Randomized Phase                              | Safety            | X               |                |
| 3.2.17           | Summary of Treatment-Emergent Adverse Events of Special Interest in Randomized Phase  | Safety            | X               |                |
| 3.2.18           | Overall Summary of Treatment-Emergent Adverse Events in All Ruxolitinib Treated Phase   | Safety            | X               |                |
| 3.2.19           | Summary of Treatment-Emergent Adverse Events by MedDRA System Organ Class and Preferred Term in All Ruxolitinib Treated Phase                             | Safety            | X               |                |
| 3.2.20           | Summary of Treatment-Emergent Adverse Events by MedDRA Preferred Term in Decreasing Order of Frequency in All Ruxolitinib Treated Phase                   | Safety            | X               |                |
| 3.2.21           | Summary of Treatment-Emergent Adverse Events by MedDRA System Organ Class, Preferred Term, and Worst CTCAE Grade in All Ruxolitinib Treated Phase         | Safety            | X               |                |
| 3.2.22           | Summary of Grade 3 or Higher Treatment-Emergent Adverse Events by MedDRA System Organ Class and Preferred Term in All Ruxolitinib Treated Phase           | Safety            | X               |                |
| 3.2.23           | Summary of Treatment-Related Adverse Events by MedDRA System Organ Class and Preferred Term in All Ruxolitinib Treated Phase                              | Safety            | X               |                |

| Table No.              | Title   | Population | Standard | In-Text |
|-------------------------------|--|-------------------|-----------------|----------------|
| 3.2.24                        | Summary of Treatment-Related Adverse Events by MedDRA System Organ Class, Preferred Term, and Worst CTCAE Grade in All Ruxolitinib Treated Phase                       | Safety            | X               |                |
| 3.2.25                        | Summary of Treatment-Emergent Adverse Events With a Fatal Outcome by MedDRA System Organ Class and Preferred Term in All Ruxolitinib Treated Phase                     | Safety            | X               |                |
| 3.2.26                        | Summary of Treatment-Emergent Serious Adverse Events by MedDRA System Organ Class and Preferred Term in All Ruxolitinib Treated Phase                                  | Safety            | X               |                |
| 3.2.27                        | Summary of Treatment-Emergent Serious Adverse Events by MedDRA Preferred Term in Decreasing Order of Frequency in All Ruxolitinib Treated Phase                        | Safety            | X               |                |
| 3.2.28                        | Summary of Treatment-Related Serious Adverse Events by MedDRA System Organ Class and Preferred Term in All Ruxolitinib Treated Phase                                   | Safety            | X               |                |
| 3.2.29                        | Summary of Treatment-Emergent Adverse Events Leading to Dose Interruption by MedDRA System Organ Class and Preferred Term in All Ruxolitinib Treated Phase             | Safety            | X               |                |
| 3.2.30                        | Summary of Treatment-Emergent Adverse Events Leading to Dose Reduction by MedDRA System Organ Class and Preferred Term in All Ruxolitinib Treated Phase                | Safety            | X               |                |
| 3.2.31                        | Summary of Treatment-Emergent Adverse Events Leading to Discontinuation of Study Drug by MedDRA System Organ Class and Preferred Term in All Ruxolitinib Treated Phase | Safety            | X               |                |
| 3.2.32                        | Summary of Treatment-Emergent Adverse Events Leading to Withdrawal From the Study by MedDRA System Organ Class and Preferred Term in All Ruxolitinib Treated Phase     | Safety            | X               |                |
| 3.2.33                        | Summary of Treatment-Emergent Non-Serious Adverse Events by MedDRA System Organ Class and Preferred Term in All Ruxolitinib Treated Phase                              | Safety            | X               |                |
| 3.2.34                        | Summary of Treatment-Emergent Adverse Events of Special Interest in All Ruxolitinib Treated Phase  | Safety            | X               |                |
| Laboratory Assessments |  |                   |                 |                |
| 3.3.1                         | Summary of Laboratory Values - Hematology  | Safety            | X               |                |
| 3.3.2                         | Summary of Laboratory Values - Hematology for Crossover Subjects   | Safety            | X               |                |
| 3.3.3                         | Shift Summary of Hematology Values in CTC Grade - To the Worst Abnormal Value in Randomized Phase  | Safety            | X               |                |
| 3.3.4                         | Shift Summary of Hematology Values in CTC Grade - To the Worst Abnormal Value in All Ruxolitinib Treated Phase   | Safety            | X               |                |
| 3.3.5                         | Summary of Laboratory Values - Chemistry   | Safety            | X               |                |
| 3.3.6                         | Summary of Laboratory Values - Chemistry for Crossover Subjects  | Safety            | X               |                |
| 3.3.7                         | Shift Summary of Chemistry Values in CTC Grade - To the Worst Abnormal Value in Randomized Phase   | Safety            | X               |                |
| 3.3.8                         | Shift Summary of Chemistry Values in CTC Grade - To the Worst Abnormal Value in All Ruxolitinib Treated Phase  | Safety            | X               |                |
| 3.3.9                         | Summary of Laboratory Values - Urinalysis  | Safety            | X               |                |

| Table No.          | Title  | Population | Standard | In-Text |
|--------------------|--|------------|----------|---------|
| 3.3.10             | Summary of Laboratory Values - Urinalysis for Crossover Subjects | Safety     | X        |         |
| Vital Signs |  |            |          |         |
| 3.4.1              | Summary of Systolic Blood Pressure                               | Safety     | X        |         |
| 3.4.2              | Summary of Systolic Blood Pressure for Crossover Subjects        | Safety     | X        |         |
| 3.4.3              | Summary of Diastolic Blood Pressure                              | Safety     | X        |         |
| 3.4.4              | Summary of Diastolic Blood Pressure for Crossover Subjects       | Safety     | X        |         |
| 3.4.5              | Summary of Heart Rate  | Safety     | X        |         |
| 3.4.6              | Summary of Heart Rate for Crossover Subjects                     | Safety     | X        |         |
| 3.4.7              | Summary of Body Temperature                                      | Safety     | X        |         |
| 3.4.8              | Summary of Body Temperature for Crossover Subjects               | Safety     | X        |         |
| 3.4.9              | Summary of Respiration Rate                                      | Safety     | X        |         |
| 3.4.10             | Summary of Respiration Rate for Crossover Subjects               | Safety     | X        |         |
| 3.4.11             | Summary of Weight  | Safety     | X        |         |
| 3.4.12             | Summary of Weight for Crossover Subjects                         | Safety     | X        |         |

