### **3.2. Control of Type I Error**

The level of significance for the primary endpoint is 2-sided 0.05. The family wise alpha level will be controlled at 0.05 and will be controlled using a fixed sequential testing procedure. The proportion of subjects who achieve CR or PR at Week 32, as defined by ELN 2013 response criteria, will only be formally tested if the hypothesis for the primary endpoint is rejected. No other efficacy endpoints will be included in the alpha control.

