#### **7.2.3.1 Additional Sensitivity Analyses for Primary Endpoint**

Excess missing data will affect the validity of the study. All efforts will be made to minimize missing data. In addition, sensitivity analysis will be conducted to assess the impact of the missing data if  $> 10\%$  of subjects with primary endpoint status missing.

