### 7.2.3.1.1. Primary Endpoint Status Determination

The primary efficacy endpoint is the proportion of subjects who achieve a simultaneous reduction of platelet counts to  $< 600 \times 10^9/L$  and of WBC counts to  $< 10 \times 10^9/L$  for at least 80% (6 out of 7 consecutive visits) of biweekly assessments for 12 consecutive weeks between Week 32 and Week 52. There are 5 consecutive 12-week periods: Weeks 32 to 44, Weeks 34 to 46, Weeks 36 to 48, Weeks 38 to 50 and Weeks 40 to 52.

For each of the 5 consecutive 12-week periods, 7 scheduled biweekly visits are planned. A subject will be flagged as "Responder," "Nonresponder," or "Nondeterminable" as the following at each period:

- If a subject has  $\geq 6$  visits with platelet counts  $< 600 \times 10^9/L$  and WBC counts  $< 10 \times 10^9/L$ , then this subject is flagged as Responder at this period.
- If a subject has  $\geq 2$  visits with platelet count  $\geq 600 \times 10^9/L$  or WBC counts  $\geq 10 \times 10^9/L$ , then this subject is flagged as Nonresponder at this period.
- If the above 2 conditions are not met for a subject, then this subject is flagged as nondeterminable at this period.
- If a subject discontinued from the study treatment between Weeks 32 and 52, the response status for the periods after the treatment discontinuation will not be assessed.

The primary endpoint status for a subject can be determined as the following:

- If any period is deemed as Responder for a subject, then the primary endpoint status of this subject is Responder.
- If "Nonresponder" is flagged in all assessed periods for a subject, then the primary endpoint status of this subject is Nonresponder.
- Otherwise, the primary endpoint status for a subject cannot be determined and the value will be missing.

If a subject discontinued from the study treatment before Week 32, then the primary endpoint status of this subject is missing.

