### 7.2.3.1.4. Multiple Imputation

For each missing value of the primary endpoint status, a list of  $m$  ( $m = 5$ ) imputed values will be generated through multiple imputation method and replaced for the missing value. The primary endpoint status is a dichotomous variable with values of responder and nonresponder; thus, logistic regression imputation method will be used to impute missing values of the primary endpoint status. In the logistic regression imputation method, a logistic regression model is fitted for the primary endpoint status variable with a set of covariates constructed from the effects, where the set of covariates is listed in Section 7.2.3.1.3 plus treatment group. The sample SAS code for multiple imputation is included in [Appendix E](#).

After multiple imputation,  $m$  imputed complete datasets will be generated. For each of  $m$  imputed datasets, the proportion of subjects who achieve primary endpoint will be summarized by treatment group. The combined results from  $m$  imputed data on proportion of subjects who achieve the primary endpoint will also be summarized, where the combined proportion is the average of the estimated proportion from each of  $m$  imputed datasets.

For each of  $m$  imputed datasets, a logistic regression model will be fitted for the primary endpoint status variable with treatment group, JAK2V617F mutation status, screening platelet count ( $\geq 1000 \times 10^9/L$  or  $< 1000 \times 10^9/L$ ), and prior anagrelide use (yes vs no) as covariates.

Additional multiple imputation methods may be explored to assist assessing the robustness of the primary endpoint due to missing value.

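### Five imputations leave avoidable seed-to-seed noise in the p-value of the primary endpoint's missing-data sensitivity analysis

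*SAP*

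**What the plan says.** SAP 7.2.3.1 makes the analysis conditional: a "sensitivity analysis will be conducted to assess the impact of the missing data if" more than 10% of subjects lack a primary endpoint status. SAP 7.2.3.1.1 defines who lacks one. Early stoppers are included: "If a subject discontinued from the study treatment before Week 32, then the primary endpoint status of this subject is missing". So are subjects seen after Week 32 whose visits do not settle the matter either way.

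SAP 7.2.3.1.4 sets m = 5: for each missing status, five "imputed values will be generated through multiple imputation method and replaced for the missing value". In each completed dataset "a logistic regression model will be fitted for the primary endpoint status variable with treatment group, JAK2V617F mutation status", screening platelet count and prior anagrelide use. Appendix E agrees with the text ("NIMPUTE=5 SEED=8554633463") and pools the fits in PROC MIANALYZE with "MODELEFFECTS Treat JAK2V617F plat_screen Anagre_use", which produces a pooled treatment estimate and test.

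The SAP gives no reason for choosing five, no Monte Carlo error target, no rule for raising m and no check across seeds. SAP 7.2.3.1.4 adds only that further imputation methods may be explored. On significance, SAP 3.2 says "The level of significance for the primary endpoint is 2-sided 0.05" and puts only Week 32 remission behind it in the testing sequence. No criterion is attached to the imputation analysis.

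**The concern.** Five imputations estimate the between-imputation variance on 4 degrees of freedom. That variance enters the pooled standard error and the t reference distribution, so the p-value moves when the same data are imputed under another seed. The 10% trigger means the analysis is never used where missingness is low enough for this to be negligible.

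It is also the only prespecified re-analysis aimed at missing primary endpoint status. The per-protocol and mutation-status analyses in SAP 7.2.3 address other questions, and SAP 7.2.3.1.2 only tabulates the missing data. If the pooled p-value falls near 0.05, one arbitrary number could decide whether the primary result is described as robust to missing data.

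**Working it through.** m = 5 is a specification, so there is no calculated figure to reproduce.

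**Inputs from the documents.** 60 per arm and response rates of 30% vs 5% (SAP 3.3); trigger above 10% (SAP 7.2.3.1), that is, at least 13 of 120 subjects; m = 5 (SAP 7.2.3.1.4 and Appendix E).

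**Assumed inputs.** Missing rates of 12%, 20%, 30% and 40%; data missing completely at random; stratum prevalences of 50%, 35% and 25%; one continuous covariate standing in for the last blood count.

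**1. Point estimate.** Relative efficiency is 1/(1 + FMI/m), where FMI is the fraction of missing information. At m = 5:
- FMI 0.1: 1/(1 + 0.02) = 0.98
- FMI 0.3: 1/(1 + 0.06) = 0.94
- FMI 0.5: 1/(1 + 0.10) = 0.91

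Little is lost here.

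**2. Noise in the variance.** The relative SD of the between-imputation variance is roughly √(2/(m − 1)): √(2/4) = 0.71 at m = 5, √(2/49) = 0.20 at m = 50 and √(2/99) = 0.14 at m = 100.

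**3. Noise in the test statistic.** From the point estimate alone, the seed-to-seed SD of the pooled z is about √(FMI/m). The median simulated FMI was 0.12, 0.20 and 0.28 at 12%, 20% and 30% missing:

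| Missing | m = 5 | m = 50 | m = 100 |
|---|---|---|---|
| 12% | √(0.12/5) = 0.15 | 0.05 | 0.03 |
| 20% | √(0.20/5) = 0.20 | 0.06 | 0.04 |
| 30% | √(0.28/5) = 0.24 | 0.07 | 0.05 |

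Direct simulation at 30% missing gave 0.28 at m = 5 and 0.08 at m = 50. These are slightly higher, as expected once noise in the standard error is included.

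**4. Chance that two seeds disagree on p < 0.05.** The simulation used logistic imputation, a logistic analysis with treatment and the three strata, and Rubin's rules with a t reference. A Firth-type penalty kept sparse fits finite. There were 40 trials per setting at 30% vs 5%:

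| Missing | m = 5 | m = 50 | m = 100 | Median 95% range of p over seeds, m = 5 |
|---|---|---|---|---|
| 12% | 1.8% | 0.0% | 0.0% | 0.016 |
| 20% | 11% | 1.0% | 0.1% | 0.044 |
| 30% | 22% | 0.8% | 0.0% | 0.091 |
| 40% | 30% | 10% | 6.4% | 0.186 |

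Simpler simulations that pool an unadjusted log odds ratio widen the m = 5 figures to about 2-5%, 8-11% and 16-22% at 12%, 20% and 30% missing, and the m = 100 figures to about 0-3%. At a smaller effect (25% vs 8%, 12% missing) the logistic simulation gave 14% at m = 5 and 1.2% at m = 100. The m = 100 column in the table draws subsets from 600 imputations and slightly understates the variation.

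**5. Two worked datasets, chosen because their p-values lie near 0.05.** These used fresh imputations, with 200 seeds at m = 5 and 60 seeds at m = 50 and m = 100.
- 14/120 = 11.7% missing, observed responders 12/54 vs 3/52. At m = 5, p ran from 0.013 to 0.085, with 15% of seeds at or above 0.05. At m = 50 it ran from 0.020 to 0.042, and at m = 100 from 0.024 to 0.037.
- 30/120 = 25% missing, observed responders 13/45 vs 3/45. At m = 5, p ran from 0.003 to 0.133, with 17.5% of seeds at or above 0.05. At m = 50 it ran from 0.014 to 0.037, and at m = 100 from 0.015 to 0.033.

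Every seed at m = 50 and m = 100 gave p < 0.05 in both datasets. They show what can happen near the threshold, not how often it does.

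**The case against.** Much of the case on the other side stands.

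- **The seed is fixed in advance.** The result is reproducible and the seed cannot be chosen after seeing the data. What remains is that the prespecified number is arbitrary and may still settle a borderline reading.
- **The primary test is untouched.** Under SAP 7.2.1 a missing visit counts as not controlled, and stopping treatment without response counts as nonresponse. No imputation enters. A reader might infer that another seed could overturn the primary result; the documents do not support that.
- **No p < 0.05 rule applies.** The analysis is conditional and outside the alpha-controlled sequence, and averaged imputed proportions are reported as well. A reader might infer a formal robustness test that could pass or fail; the SAP defines none.
- **Crossing the trigger does not by itself make m = 5 inadequate.** Just above 10% missing, at the design effect, two seeds disagree in only about 2-5% of trials. Disagreement becomes common at 20-30% missing or with a smaller effect.
- **Larger instability figures can be produced.** Counting a trial as unstable if any of 12 seeds differs gave 7%, 20% and 45% at 12%, 20% and 30% missing in one simulation. That count rises with the number of seeds tried and is not the chance that one rerun reverses the finding.
- **The simulations are not the SAP's model.** SAP 7.2.3.1.3 also uses last platelet, WBC and hemoglobin values, infection, and trauma or surgery. In a simple check, one strongly predictive covariate lowered two-seed disagreement at 30% missing from 19% to 14%, with little change at 12-20%. The direction holds, but the exact figures do not transfer.

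**Conclusion.** The point holds as a minor one. With m = 5 the estimate is adequate, but the pooled standard error and p-value contain Monte Carlo noise that a larger m largely removes. At the design rates, the chance that a second seed gives a different answer on p < 0.05 is about 2-5%, 8-11% and 16-22% at 12%, 20% and 30% missing, against about 0-3% at m = 100.

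These sizes rest on assumed missing rates, because neither document gives an expected dropout, and on a simplified imputation model with data missing completely at random. They bear on how a conditional sensitivity analysis is read, and not on the trial's primary conclusion.

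**What to change.** In SAP 7.2.3.1.4 change m from 5 to at least 50, preferably 100, and change NIMPUTE in Appendix E to match. Keep the prespecified seed. Report the Monte Carlo error of the pooled treatment estimate, √(B/m), where B is the between-imputation variance. This matters most if missingness is heavy: at an assumed 40% missing, two seeds still disagreed in 6.4% of simulated trials at m = 100.

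The cost is one number in two places, one extra reported quantity and seconds of computing. Design, alpha, estimand and the primary analysis stay as they are.
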